6.8.4. Continuous Glucose Monitoring

Continuous glucose monitoring (CGM) device data was collected for only cohort 3 and 4 in Study 401GSDIA01. It will be collected for all subjects in Study 401GSDIA02. Available data from both studies 401GSDIA01 and 401GSDIA02 will be included in this analysis. CGM values less than 40 mg/dL or greater than 400 mg/dL will not be included in the analysis because they are not considered as reliable values being outside the Dexcom G6 reportable range of 40-400 mg/dL.

Percentage of glucose values in different glucose ranges (<54, <60, <70, 60-120, 70-120, >120 mg/dL) together with cornstarch intake (in grams) will be plotted by visit for each subject along with the actual cornstarch use at the visit. CGM data in 4 weeks prior to the visit will be used to calculate the percentage of glucose values in any range. Percentage of glucose values in any glucose range for a visit is calculated as number of glucose values in that range in a 4-week period prior to the visit, divided by total number of glucose values in that 4-week period and multiplied by 100. Further, mean percentage of glucose values in different glucose ranges (<54, <60, <70, 60-120, 70-120, >120 mg/dL) together with mean actual cornstarch intake (in grams) will be plotted by visit for each cohort.

Time spent below 70 mg/dL in 4 weeks prior to the visit will be plotted by visit for each subject. Time duration (in minutes) of glucose values spent in a range is calculated as sum of all the time intervals where glucose value is in that range. Time interval for any glucose value is calculated as the difference between collection time of that glucose value and the next collection time. Glucose values are usually collected approximately every 5 minutes, however if the glucose value is missing at any collection time the last available glucose value prior to the collection time will be carried forward if that value is collected within 15 minutes.

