Number and total duration of hypoglycemic events in 4 weeks prior to the visit will be plotted by visit for each subject together with actual cornstarch use at a visit. A hypoglycemic event is defined as a series of at least two sensor glucose values less than 54 mg/dL that are at least 15 minutes apart with no intervening values of 54 mg/dL or more. The end of a hypoglycemic event is defined as at least two sensor glucose values > 70 mg/dL that are at least 15 minutes apart with no intervening values <70 mg/dL. Similar plots will be provided for nocturnal hypoglycemic events. Summary of number and duration of hypoglycemic events in 4 weeks prior to the visit will be provided.

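### SAP 6.8.4 reports CGM hypoglycaemic event number and duration, and minutes below 70 mg/dL, as unscaled 4-week totals, so they depend on how complete the CGM record is

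*SAP*

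**What the plan says.** SAP 6.8.4 (Continuous Glucose Monitoring) takes the 4 weeks of CGM data before each visit and derives three kinds of output.

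- **Percentage of values in range**, including below 54, 60 and 70 mg/dL. The denominator is the number of readings available in the window. It is plotted by subject and as cohort means, with cornstarch intake.
- **Minutes below 70.** "Time spent below 70 mg/dL in 4 weeks prior to the visit will be plotted by visit for each subject". Duration in a range "is calculated as sum of all the time intervals where glucose value is in that range". There is no denominator, and no cornstarch overlay is specified.
- **Hypoglycaemic events.** "Number and total duration of hypoglycemic events in 4 weeks prior to the visit will be plotted by visit for each subject", with actual cornstarch use; nocturnal events get similar plots. In addition, "Summary of number and duration of hypoglycemic events in 4 weeks prior to the visit will be provided". There is no denominator.

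The interval rule is: "Time interval for any glucose value is calculated as the difference between collection time of that glucose value and the next collection time". The next sentence says "Glucose values are usually collected approximately every 5 minutes" and that, where a value is missing at a collection time, "the last available glucose value prior to the collection time will be carried forward if that value is collected within 15 minutes".

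An event needs "at least two sensor glucose values less than 54 mg/dL that are at least 15 minutes apart", with nothing at or above 54 in between. It ends with two values above 70 at least 15 minutes apart, with nothing below 70 in between. Readings below 40 or above 400 mg/dL are left out of the analysis.

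Protocol 10.4.2 asks subjects to bring 28 days of data to each visit. For remote or missed visits this is only the ideal. The receiver is to stay within range of the sensor where possible. Neither document sets a minimum amount of CGM data for a visit to be reported.

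**The concern.** A count or a sum of minutes over a fixed 4-week window can be compared between visits only if the window is equally well observed each time. Follow-up in this study lasts up to 5 further years, and the protocol itself foresees imperfect data capture. If wear falls over that time, events are missed and the plots show fewer of them with no change in the subject.

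This matters most for the event outputs. They are drawn beside cornstarch use, so a fall in wear could be taken for stable or better glucose control as cornstarch is reduced. They also go into a summary that, under SAP 6.1, is shown by cohort. Cohorts in Study 401GSDIA01 had 3 subjects each, so one poorly recorded subject can move a cohort mean. Glucose homeostasis is a tertiary objective.

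A second problem is reproducibility. If two programmers can read the interval and event rules differently, the same data can give different minutes, event counts and durations.

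**Working it through.** The plan states no CGM result, wear figure or sample-size calculation, so there is no figure to reproduce. The check applies the SAP's own definitions to assumed values.

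**Inputs.** From SAP 6.8.4: a 4-week window, readings about every 5 minutes and a 15-minute carry-forward limit. Assumed, because the documents do not give them: the true share of time below 70, the true number of events and the wear fraction.

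**1. Effect of wear on the totals.** Window = 28 × 24 × 60 = 40,320 minutes, or 40,320 / 5 = 8,064 readings at full wear. If unobserved time is not attributed to any range and gaps are unrelated to glucose:

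expected minutes below 70 = 40,320 × true share × wear

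expected events ≈ true events × wear

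| Wear | Minutes below 70 (true share 5%) | Percentage of values below 70 | Events (true number 6) |
|---|---|---|---|
| 100% | 2,016 | 5.0 | 6.0 |
| 90% | 1,814 | 5.0 | 5.4 |
| 70% | 1,411 | 5.0 | 4.2 |
| 50% | 1,008 | 5.0 | 3.0 |
| 25% | 504 | 5.0 | 1.5 |

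A subject with twice the burden and half the wear gives 40,320 × 0.10 × 0.50 = 2,016 minutes. That equals 5% at full wear (40,320 × 0.05), so a twofold difference vanishes from the minutes plot. The percentage metric still shows 5% against 10%. The event column is an approximation, since it ignores gaps that cut into an event.

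In a cohort of 3 with 6 true events each, one subject at 50% wear lowers the cohort mean to (6 + 6 + 3) / 3 = 5.0.

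**2. Credit for a gap after a low value.**

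| Gap | Next 5-minute slot, 15-minute limit applied | Next stored record |
|---|---|---|
| 30 min | about 15 min | 30 min |
| 8 h | about 15 min | 480 min |
| 24 h | about 15 min | 1,440 min |

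Under the first reading the excess over a normal 5-minute interval is about 10 minutes, whatever the length of the gap.

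**3. Simulation of minutes below 70.** Assumed: 400 replicates, 5% of time below 70, episodes of mean length 40 minutes, gaps unrelated to glucose.

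| Mean wear | True minutes | With 15-minute limit | Whole gap credited |
|---|---|---|---|
| 98.5% | 1,998 | 1,970 | 2,004 |
| 94.2% | 2,025 | 1,914 | 2,041 |
| 70.5% | 2,046 | 1,448 | 2,120 |
| 37.5% | 2,011 | 773 | 2,381 |

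With the limit, the loss is (1,998 − 1,970) / 1,998 = 1.4% at 98.5% wear, (2,025 − 1,914) / 2,025 = just under 5.5% at 94.2%, and (2,046 − 1,448) / 2,046 = 29% at 70.5%. If the whole gap is credited, the mean does not fall with wear but the result becomes erratic: at 70.5% wear the SD is 1,215 minutes, against 344 for the true values.

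The correlation of the capped minutes with wear was 0.33 at 70.5% mean wear and 0.62 at 37.5%. For the percentage metric it was −0.10 and −0.02.

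**4. Event rules.** The start rule sets a minimum spacing between two low values but no maximum, so low values on either side of a long dropout could be joined into one event. The end rule needs two later values above 70. No formula is given for event duration. Removing readings below 40 creates missing values within the lowest episodes, and the rules do not say how these are treated.

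**The case against.** The strongest reply has four parts.

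*The gap rule already has a limit.* The sentence after the interval rule restricts carry-forward to 15 minutes and serves the same metric. This stands as far as it goes. A reader might infer from the interval sentence alone that a whole sensor gap is credited to the last value, adding 480 or 1,440 minutes. The documents do not establish that; it is one of two readings. What remains is that the SAP does not say whether the next collection time is a scheduled slot or a stored record, nor that time beyond 15 minutes is dropped.

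*Time below 70 has a scaled counterpart.* This also stands. The percentage of values below 70 uses available readings, so a fall in minutes due only to wear would not appear there. The minutes plot has no cornstarch overlay either; the overlays are on the percentage and event plots. The reply does not reach event number and duration, which have no scaled version.

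*Wear may be high.* Protocol 10.4.2 asks for 28 days of data, pairing with the study receiver and weekly uploads, and 10.4.3 offers morning glucose when CGM cannot be used. A reader might infer that these outputs measure completeness as much as hypoglycaemia. The documents give no wear data to support that, and at high wear the loss is small. But no output showing wear is planned, so a reader of the results could not tell.

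*The stakes are low.* CGM is described as supplemental, all analyses are descriptive, and the tertiary glucose endpoint names serum glucose. This stands and limits the weight of the point.

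**Conclusion.** The point holds. Event number, event duration and minutes below 70 are raw 4-week totals with no scaling to valid CGM time and no minimum wear. The main defect that nothing else in the section corrects lies in the event outputs: they have no scaled version, they are read against cornstarch use, and they have no rule for gaps. For minutes below 70, the scaled percentage largely covers the wear problem, and what is left is the ambiguous interval rule.

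The size depends on wear, which is unknown. It is about 1% to 5% of minutes at 94% to 98% wear and about half at 50% wear, with events falling roughly in step. This assumes that gaps are unrelated to glucose and that gap time is not credited. The direction for event duration cannot be stated, because a gap could shorten an event or be counted inside it. No primary or secondary endpoint is affected.

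**What to change.** In SAP 6.8.4:

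1. Report event number, event duration (including nocturnal events) and minutes below 70 per 24 hours, or per 28 days, of valid CGM time.
2. Show percent wear for each subject and visit beside these outputs, and flag visits below a pre-specified minimum.
3. Define the next collection time, and state that time more than 15 minutes after the last valid reading is not attributed to any range.
4. Pre-specify one rule for gaps within events, covering start, end and duration, and say how deleted readings below 40 mg/dL are treated under it. Any choice has a cost: closing an event at a gap may shorten or split it, while bridging the gap may lengthen or merge events. It should therefore be fixed before the data are summarised.

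The cost is SAP wording and a little more programming, using data already collected. Some low-wear visits will be flagged. Protocol 12.5.3 says only that CGM data will be summarised, so its text does not conflict with these changes.

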6.8.5. Morning Glucose Levels

If a subject is unable to use the assigned CGM, the subject should collect morning glucose levels at least 2 mornings per week throughout the study. Data from both studies 401GSDIA01 and 401GSDIA02 will be included in this analysis.

Individual morning glucose levels will be summarized by visit and provided in the listings. Data collected in 4 weeks prior to the visit will be included in the analysis. Plots for individual patient profile of weekly mean morning glucose level and overnight cornstarch dose (as reported in morning glucose level eCRF) will also be presented.

6.8.6. Liver Magnetic Resonance Imaging and Ultrasound

Data from both studies 401GSDIA01 and 401GSDIA02 will be included in this analysis.

Descriptive statistics for liver MRI results, including mean proton density fat fraction (PDFF) across liver segments (%) and liver volume (ml), and change from Study 401GSDIA01 baseline values will be summarized by study visit. Each MRI will be interpreted as “normal”, “abnormal not clinically significant”, or “abnormal clinically significant”. The interpretation of the MRI data will be summarized by study visit using a shift table. A listing of all MRI results including the interpretation will be provided.

Descriptive statistics for liver ultrasound results (interpreted as “normal”, “abnormal not clinically significant”, or “abnormal clinically significant”) will be summarized by study visit. A listing of liver ultrasound results will be provided.

6.8.7. Health-Related Quality of Life and Sleep Quality

The observed values over time and change from Study 401GSDIA01 baseline values will be summarized for quality-of-life related measures. Data from both studies 401GSDIA01 and 401GSDIA02 will be included in this analysis.

Listings for the HRQoL (PROMIS-29, PROMIS Social Isolation, PGI-S, and PGI-C) and sleep quality (PSQI) assessments will be provided. Summary of percent change from baseline in actual cornstarch intake by PGIC will be provided by visit.

Findings from endpoint outcomes interview (Year 2 - exit interview) will be described in a qualitative manner.

6.9. Safety Analysis

The safety analysis will be performed using the FAS. The safety parameters will include AEs, SAEs, vital sign measurements, physical examination findings, electrocardiogram (ECG) results, subject reported symptomatic hypoglycemic events, clinical laboratory assessments (clinical chemistry [including liver function tests], hematology, coagulation panel, and urinalysis), vector shedding, vector genome determination, measurement of neutralizing antibody titer to AAV8, measurement of AAV8 binding antibody immunoglobulin G (IgG), assessment of any cell-mediated immune responses to AAV8 and G6Pase, and measurement of anti-G6Pase antibodies.

6.9.1. Adverse Events

Adverse events will be coded by system organ class (SOC) and preferred term (PT) using the current version of Medical Dictionary for Regulatory Activities.

An AE (classified by preferred term) will be considered a treatment emergent adverse event (TEAE) if it occurred on or after the first dose of IP.

AEs from both studies 401GSDIA01 and 401GSDIA02 will be combined for this analysis. Further, AEs from Study 401GSDIA02 will also be summarized separately.

Subject incidence of TEAEs will be tabulated as the follows. The number of events will also be included.:

- Summary of TEAEs
- TEAEs by SOC and PT
- Related TEAEs by SOC and PT

- Serious Related TEAEs by SOC and PT
- Grade 3 or 4 TEAEs by SOC and PT
- Fatal TEAEs by SOC and PT
- TEAEs leading to discontinuation of study by SOC and PT
- TEAEs by PT
- TEAEs by PT and greatest severity
- TEAEs by their time of occurrence (<1, 1-2, 2-3, 3-4, 4-5, 5-6 years since the IP administration)

The severity will be based on the most current version of CTCAE. If an AE cannot be graded based on CTCAE, the investigator will assign a severity based on 1 = mild, 2 = moderate, 3 = severe, 4 = life threatening, and 5 = death. Detailed listings for all AEs, serious TEAEs, TEAEs leading to the discontinuation of study, and death will also be generated.

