11.1.3. Relationship of Adverse Events to Investigational Product

The Investigator will assess the potential relationship of the AE to IP using the following descriptions.

Categories of attributions for “unrelated” events:

- **Unrelated:** This category applies to an AE that *is clearly not related* to the investigational agent/procedure.

Categories of attributions for “related” events:

- **Possibly Related:** This category applies to an AE that *may be related* to the investigational agent/procedure.
- **Probably Related:** This category applies to an AE that *is likely related* to the investigational agent/procedure.
- **Definitely Related:** This category applies to an AE that *is clearly related* to the investigational agent/procedure.

For the purposes of reporting to regulatory agencies, AEs deemed as definitely, probably or possibly related will be considered related.

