12.4. Safety Analyses

12.4.1. Adverse Events

All AEs will be coded according to the Medical Dictionary for Regulatory Activities. The incidence of AEs will be summarized for each cohort and overall by system organ class and preferred term. Additionally, AEs may be summarized for each cohort and overall by severity and relationship to IP, if applicable. Serious AEs will be presented for each cohort and overall by relationship to IP. Summary tables will present the total numbers of AEs as well as the number of subjects with AE incidence by system organ class and preferred term. For incidence of relationship to IP, subjects will be counted only once, in the category of the strongest relationship to IP within each system organ class/preferred term.

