2. STUDY OBJECTIVE(S)

2.1. Primary Objective(s) and Endpoint(s)

The primary objective of the study is as follows:

- To determine the long-term safety of DTX401 following a single IV dose in adults with GSDIa

The primary endpoint of this study is as follows:

- The incidence of AEs and SAEs for each cohort and overall assessed by severity and relationship to IP

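### The SAP's only serious-event incidence table is limited to related events, although SAE incidence by relationship is part of the primary endpoint and a protocol commitment

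*SAP*

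**What the plan says.** Protocol 12.1.1 and SAP 2.1 define the primary endpoint in the same words: "The incidence of AEs and SAEs for each cohort and overall assessed by severity and relationship to IP". SAEs are a named component of it.

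Protocol 12.4.1 then makes a firm statement about serious events: "Serious AEs will be presented for each cohort and overall by relationship to IP". For AEs in general, the breakdown by severity and relationship is only permitted, where applicable. The same section sets a counting rule for relationship: "For incidence of relationship to IP, subjects will be counted only once, in the category of the strongest relationship to IP", applied within system organ class and preferred term. Protocol 11.1.3 has four relationship categories: unrelated, possibly, probably and definitely related. For reporting to regulators, "AEs deemed as definitely, probably or possibly related will be considered related".

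SAP 6.9.1 names ten TEAE tabulations. One is specific to serious events, and it is restricted to related ones: "Serious Related TEAEs by SOC and PT". The section also promises an overview, "Summary of TEAEs", without saying what rows it holds, and an all-cause table of deaths, "Fatal TEAEs by SOC and PT". Serious events of any cause are named once, under listings: "Detailed listings for all AEs, serious TEAEs, TEAEs leading to the discontinuation of study, and death will also be generated".

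SAP Section 7, which is meant to record departures from the protocol analysis, reads as not applicable. SAP Section 8 leaves the list of tables to a separate shell document.

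**The concern.** The protocol asks for serious events split by relationship, which requires both sides of the split and therefore the total. The SAP names a table for one side only. Following the SAP as written would pass the SAE component of the primary endpoint through a causality filter before it is tabulated as serious.

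That filter is weak in this setting. There is no control group (Protocol 7.2), no blinding (Protocol 9.8.2) and no Data Monitoring Committee (Protocol 11.2), and relatedness is the investigator's judgement (Protocol 11.1.3). Protocol 5.1 describes serious complications of the disease itself, so a serious event can readily be put down to GSDIa. All-cause SAE incidence does not depend on that judgement. It allows a reader to see whether events individually judged unrelated form a pattern.

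**Working it through.** The plan gives no figure to reproduce. The study is descriptive and its size is not based on power. The check sets what is promised against what is specified.

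**1. Coverage of the SAE component by the ten tabulations in SAP 6.9.1**

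| Needed for SAEs | Source of the need | Named table in SAP 6.9.1 |
|---|---|---|
| Incidence, any cause, by SOC and PT | Primary endpoint (incidence of SAEs) | None |
| Incidence across relationship categories | Primary endpoint; Protocol 12.4.1 | None; the related side alone is tabulated |
| Incidence by severity | Primary endpoint wording only | None specific to serious events |
| Cohort and overall columns | Primary endpoint; Protocol 12.4.1 | Supplied by SAP 6.1 for every summary table |

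**2. Whether other tables fill the gap**

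- The all-TEAE tables have no causality filter. A TEAE is any AE on or after dosing, and every event in this follow-up study is after dosing, so every SAE recorded here is counted in them. They do not separate serious from non-serious events.
- The Grade 3 or 4 table also has no causality filter, but it selects on severity. Protocol 11.1.2 itself distinguishes severity from seriousness.
- The fatal and discontinuation tables are all-cause, but each captures only those SAEs that meet its criterion.
- The overview may carry a row for serious TEAEs; the SAP neither states nor excludes it. Such a row would give overall SAE incidence, but not the SOC and PT detail or, by itself, the relationship split.
- The listing contains every serious TEAE, but a listing is not an incidence summary.

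**3. Size**

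Inputs: 12 subjects in four cohorts of 3 (Protocol 5.4), assuming all entered the follow-up study. Cohorts 2 to 4 combined are then 3 × 3 = 9 subjects.

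Let *u* be the number of subjects in a column of size *n* whose only SAEs were judged unrelated. All-cause serious incidence minus the incidence shown in the related-only table is *u/n*.

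- Overall, *u* = 1: 1/12 = 8.3 percentage points.
- Dose 2 combined, *u* = 1: 1/9 = 11.1 points.
- One cohort, *u* = 1: 1/3 = 33.3 points.

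The documents give no value for *u*. If it is 0, no subject is missed. As a purely hypothetical case, *u* = 3 overall with no related SAEs would show 0% in the serious table against 3/12 = 25% for any cause. A subject with both related and unrelated SAEs does appear in the related-only table, but the preferred terms of the unrelated events do not.

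**The case against.** The best counter-argument is that little is lost. At most about 12 subjects are followed, nothing is tested, and serious TEAEs are listed in full, so a reader can count them by hand. The overview may already have a serious row, and the shells, which are not part of these documents, may hold more. All of this stands as a limit on impact. It does not supply the protocol's presentation by relationship, and a hand count from a listing does not replace a specified summary of a primary-endpoint component.

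Three stronger readings are tempting, and the documents do not support them.

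- A reader might infer that SAEs judged unrelated vanish from every incidence table. They do not: they are counted in the all-TEAE tables and, where they qualify, in the Grade 3 or 4, fatal and discontinuation tables. What is missing is their identification as serious.
- A reader might infer that SAEs are not shown by cohort. SAP 6.1 puts cohort, dose 2 combined and overall columns on all summary tables unless otherwise specified.
- A reader might infer that the SAE part of the endpoint is not analysed at all. The text supports only that the SAP names no all-cause serious table and no serious table across relationship categories.

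The protocol is also less explicit on two details. The strongest-relationship rule is stated for AE incidence by relationship generally, so applying it to SAEs is the natural reading but not a separate SAE commitment. An SAE table by severity rests on the endpoint sentence alone; the SAP does tabulate all TEAEs by greatest severity.

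**Conclusion.** The point holds as a mismatch between protocol and SAP on a component of the primary endpoint. The protocol states that serious AEs will be presented by relationship; the SAP names a table for related serious events only and declares no change. This goes beyond missing detail, because the list as written leaves all-cause and unrelated SAE incidence without a named table by SOC and PT or by relationship.

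The practical impact is moderate, given the small study and the serious TEAE listing. The per-subject sizes above assume that all 12 treated subjects enrolled; with fewer, each subject weighs more. The conclusion rests on the text of the two documents and would soften if the shells already contain the missing tables, though the SAP should still name them.

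**What to change.** In SAP 6.9.1:

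1. Add serious TEAEs by SOC and PT, regardless of causality.
2. Add serious TEAEs by strongest relationship to IP, with each subject counted once within SOC and PT, following Protocol 12.4.1. SAP Appendix 1 assigns missing causality simply as related, so state where such events fall among the three related categories.
3. Keep the related-only serious table as a subset of the first.
4. State the rows of the overview table, including one for serious TEAEs.

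The existing rule in SAP 6.1 already gives these tables the cohort, dose 2 combined and overall columns. Serious TEAEs by greatest severity would be an optional addition that follows from the endpoint wording. If the sponsor prefers not to add the tables, SAP Section 7 should declare and justify the narrowing.

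The cost is one or two standard tables. No new data are needed: Protocol 11.1.4.1 already requires severity and relationship for every AE, and serious TEAEs are already identified for the listing.
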